3.0 Background

3.1 Summarize the relevant prior research on this topic and gaps in current knowledge within the field of study:

21-1072 Validation and application of wearable sensors for capturing responses to losses of balance

Falls are the leading cause of injuries among older adults. An estimated 60% of falls among community-dwelling older adults are due to LOBs induced by tripping or slipping [Berg 1997]. Laboratory studies have shown that these falls generally result from an age-related decline in balance recovery ability after an LOB [Pavel 2007; van Dieen 2005]. However, technical challenges with capturing the kinematics of these events outside the lab has resulted in at least two knowledge gaps that limit progress in fall prevention research. First, there is a need to validate the use of wearable sensors (that can be used outside the lab in the real-world) by comparing their measurements with a gold-standard laboratory system. Second, it is unclear if gait and tripping/slipping events differ meaningfully between the laboratory and real-world. Laboratory trips and slips are contrived, highly-controlled, and often not unexpected, and likely result in more stereotypical LOB responses. Real-world trips and slips are typically unexpected, have more variable etiology and environmental contributions, and as a result likely elicit more variable LOB responses. Accordingly, there is a critical need to evaluate the use of wearable sensors to capture responses to LOBs both in the laboratory and in the real-world.

Multiple studies report a reduction in real-world fall risk after perturbation-balance training (PBT) [Rosenblatt 2013; Grabiner 2012; Bhatt 2012]. These studies speculate that this reduction in fall risk is due to improved responses to LOBs. An LOB is defined as an event when the postural control of the body that resists gravity (balance) is momentarily lost, and is then followed by either successful recovery of balance without a fall, or a fall. To our knowledge, no studies have shown a direct training effect of PBT on responses to real-world LOBs. Until a real-world effect is demonstrated, PBT studies reporting a reduction in falls may be confounded by concomitant changes such as in activity intensity, safe/risky behavior, and the daily living environment rather than true PBT-induced improvements in balance.

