4.0 Study Endpoints

4.1 *Describe the primary and secondary **study** endpoints. See links below for discussion of study endpoints and how they may differ from study objectives. These are most common in clinical trials but are sometimes applicable to other types of biomedical research, as well as social, behavioral, or educational research. See link below for a discussion.*

https://docs.google.com/document/d/1Wocz7K7a0hCQJPO_khh511SOQjhGDDGHzcOPRHR5Tw/edit?usp=sharing

Study endpoints for all participants will include:

- 1) measurements of body movements during responses to LOBs after lab-induced trips and slips
- 2) two or three weeks of using wearable sensors to measure body movements during responses to LOBs after naturally-occurring trips and slips during daily life
- 3) during the two or three weeks of using wearable sensors, participants will also use a digital voice recorder to record a description of the context of each real-world LOB. Specifically, participants will be asked to make a short recording

21-1072 Validation and application of wearable sensors for capturing responses to losses of balance

after each LOB to describe (1) what they were doing at the time (e.g., “I was walking across my living room”), (2) how they lost their balance (e.g., “I tripped over my dog”), (3) why they lost their balance (e.g., “my dog ran in front of me to bark at the mailman”), and (4) the results of LOB (e.g., “I fell, or did not fall, as a result”).

4.2 *Describe any primary or secondary safety endpoints. These should be included for all studies that are greater than minimal risk. (Minimal risk: The probability and magnitude of harm or discomfort anticipated in the research that are not greater in and of themselves than those ordinarily encountered in daily life or during the performance of routine physical or psychological examinations or tests.):*

No safety endpoint is included while using wearable sensors in the real-world during daily life because the use of the wearable sensors does not increase risk above that normally experienced during every day life.

During balance training (among balance training participants), safety endpoints will include number of times the spotter is needed to provide support to the participant during training, and the number of times the participant is fully supported by the harness during measurements of responses to lab-induced LOBs.

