5.0 Study Design and Statistical Analysis Plan

5.1 *Describe the basic study design/approach (e.g., qualitative study using five focus groups of first year students to describe assimilation into the university community; randomized controlled trial of a behavioral change intervention to increase dietary intake of whole grains; pre- post-test evaluation of new pedagogical techniques to improve adult literacy):*

For our primary objective, a one-group repeated-measures design will be used to validate the use of wearable sensors to capture responses to LOBs. Subjects will use wearable sensors for three weeks to capture responses to naturally-occurring trips and slips during daily life. Subjects will then complete a laboratory session to capture lab-induced LOB responses simultaneously from the wearable sensors and a gold-standard optoelectronic motion capture system.

For our secondary objective, a three-group posttest-only design will be used to compare the effects of three balance training exercises on responses to LOBs after laboratory-induced trips and slips, and two weeks of naturally-occurring real-world trips and slips. Subjects will first complete three weeks of their assigned training. Subjects will then

21-1072 Validation and application of wearable sensors for capturing responses to losses of balance

complete a laboratory session to capture lab-induced LOB responses simultaneously from the wearable sensors and a gold-standard optoelectronic motion capture system. Subjects will then use wearable sensors for two weeks to capture responses to naturally-occurring trips and slips during daily life.

5.2 Describe corresponding data analysis plan/approach (e.g., content analysis of focus group transcripts; descriptive analysis followed by linear regression modeling; nonparametric analysis of pre- and post-test measures):

Hypothesis 1: LOB response measures obtained from the wearable sensors after lab-induced trips and slips will exhibit statistical agreement with the same measures simultaneously obtained from a gold-standard laboratory-based motion capture system.

To address Hypothesis 1, a Bland-Altman analysis will be used to evaluate level of agreement between the two systems. This approach will reveal any measurement bias between the two systems, and provide bounds for these differences.

Hypothesis 2: Real-world LOB responses will show greater variety than laboratory-induced LOB responses.

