To address Hypothesis 2, a repeated-measures ANOVA (with a random effect for subject) will first be used to compare means of key kinematic measures of LOB responses between environments (real-world vs lab). Second, we will compare statistical variability by examining the model residuals between real-world and lab environments using hypothesis testing (essentially Levene's test) and interval estimation to quantify potential differences in variability.

Hypothesis 3: NT and TT participants will exhibit improved LOB responses after lab-induced trips and slips compared to ST participants.

To address Hypothesis 3, response variables will be compared between NT, TT, and ST participants using a one-way ANOVA with group as the independent variable and covariates included as needed. A significant effect of group will be followed by post-hoc analysis using Dunnett's test to determine whether NT, TT, or both differ from ST.

Hypothesis 4: NT and TT participants will exhibit statistically-equivalent LOB responses after lab-induced trips and slips.

To address Hypothesis 4, agreement of response variables between NT and TT participants will be evaluated using statistical equivalence test.

A comparison between the three balance training exercises on LOB responses after any naturally-occurring real-world trips will be done qualitatively and thus not have an explicit hypotheses to be tested.

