- Participants will first complete a minimum of 10 walking trials along a 12-meter-long walkway at a self-selected speed. Instructions will be to “walk as if you have somewhere to go, and if tripped or slipped, recover your balance and continue walking.” All participants will wear the same model of rubber-soled shoes and a safety harness affixed to a ceiling-mounted track that spans the length of the walkway. After initial walking trials, trips and slips will be induced during randomly-selected trials with walking trials and rest breaks interspersed. As in our prior work, trips will be induced using a tripping obstacle that is initially concealed and level with the walkway. Upon proper placement of the foot relative to the obstacle while walking, the obstacle will be activated and quickly rise and result in a trip shortly after mid-swing. In an effort to add variety to the LOB responses, three trip obstacle heights from prior tripping studies will be used including 5, 7.5, and 10 cm. Slips will be induced using the same methods and distraction efforts as in our preliminary studies. While the participant is facing away from the walkway and distracted, a contaminant or slipping hazard applied over a 0.9×0.9 m targeted section of the walkway to induce an unexpected slip at heel strike during the next trial. In an effort to add variety to the LOB responses, three different contaminants or slipping hazards will be used including vegetable oil, soapy water, and a carpet mat on a polished vinyl floor.

Measure naturally-occurring LOB responses in the real-world:

- Participants will be briefed on how to wear and use the wearable sensors, and the investigator will give the sensors to the participants for them to wear over the subsequent three weeks (no balance training participants) or two weeks (TT, NT, and ST participants) during their daily lives. Participants will be asked to wear the sensors for at least 10 hours a day.

21-1072 Validation and application of wearable sensors for capturing responses to losses of balance

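### Hypothesis 2's variability test has no trip/slip term, so it cannot separate more variable responses from a different mix of trips and slips

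*Combined protocol and SAP*

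**What the plan says.** Hypothesis 2, under the primary objective, reads: "Real-world LOB responses will show greater variety than laboratory-induced LOB responses". Section 5.2 gives the analysis in two steps. First, "a repeated-measures ANOVA (with a random effect for subject) will first be used to compare means of key kinematic measures" between the real-world and laboratory environments. Second, "we will compare statistical variability by examining the model residuals between real-world and lab environments using hypothesis testing", described as essentially Levene's test, together with interval estimation. No term for loss-of-balance (LOB) type, stratification or by-type analysis is named. The allowance for covariates as needed appears only under Hypothesis 3.

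Both settings contain trips and slips. In the laboratory (Section 8.2), "trips and slips will be induced during randomly-selected trials with walking trials and rest breaks interspersed". For trips: "In an effort to add variety to the LOB responses, three trip obstacle heights from prior tripping studies will be used". For slips, "three different contaminants or slipping hazards will be used including vegetable oil, soapy water, and a carpet mat". The number of trips and slips per participant is not stated. The real-world mix is whatever occurs in three weeks of daily life.

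The Background (Section 3.1) gives the reason for the hypothesis: real-world events "have more variable etiology and environmental contributions, and as a result likely elicit more variable LOB responses". Section 4.1 provides a source for real-world event type: "participants will also use a digital voice recorder to record a description of the context of each real-world LOB".

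**The concern.** Trips and slips are different mechanical events. Section 8.2 describes an obstacle rising shortly after mid-swing in one case and a slippery surface met at heel strike in the other. A kinematic measure may well have different means for the two. With no type term, that gap stays in the residuals as if it were spread.

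How much it contributes depends on the mix of types. One mix is chosen by the investigators and the other is left to chance. The contrast is therefore partly a function of the laboratory design. A reader given one spread per setting could not tell more variable responses from a different proportion of trips. Nor could a reader tell a real absence of difference from one masked by the trip–slip gap. The plan does not say whether variety means spread over all events or spread within trips and within slips, and these are different quantities.

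**Working it through.** **Plan's own figure.** There is none for Hypothesis 2. Section 14.1 says no formal effect size could be determined for the primary objective. The one calculated figure, 7 per group for Hypothesis 3, reproduces (power 0.755 at 6 and 0.819 at 7) but does not bear on this point.

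**Variance algebra.** Let the within-type SD be 1 in the laboratory and r in the real world. Let D be the trip–slip mean difference in laboratory SDs and p the share of trips. Without a type term, the residual variance is about 1 + p(1−p)D² in the laboratory and r² + p(1−p)D² in the real world, each with its own p. Assume a laboratory mix of 50:50, so p(1−p) = 0.25, and a real-world mix of 80:20, so p(1−p) = 0.16. The real-world/laboratory variance ratio is

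(r² + 0.16D²) / (1 + 0.25D²)

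| r | D = 0 | D = 0.5 | D = 1 | D = 2 |
|---|---|---|---|---|
| 1.0 | 1.00 | 0.98 | 0.93 | 0.82 |
| 1.3 | 1.69 | 1.63 | 1.48 | 1.17 |
| 1.5 | 2.25 | 2.16 | 1.93 | 1.45 |

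The planned interval targets these ratios, whereas the within-type ratio is r² (1.00, 1.69, 2.25). The ratio falls below 1 only if r² − 1 < 0.09D². That means D > √(0.69/0.09) = 2.8 at r = 1.3, and D > √(1.25/0.09) = 3.7 at r = 1.5.

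**Simulation.** The 30 participants come from Section 14.1. Everything else is assumed:
- 3 trips and 3 slips each in the laboratory (Section 8.2 lists three heights and three hazards but no count);
- a Poisson number of real-world events, mean 4 each, 80% trips;
- intraclass correlation 0.3;
- median-centred Levene test at two-sided 5%, 2,000 trials per cell.

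Ranges cover two ways of forming residuals: random-intercept conditional residuals, and leverage-standardised residuals with participant as a fixed effect. Monte Carlo error is about 1 point.

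| D | Power at r = 1.3, planned | Power at r = 1.3, type-adjusted | Equal spread: planned test calls the laboratory more variable |
|---|---|---|---|
| 0 | 75–77% | 75–77% | 3% |
| 0.5 | 65–68% | 74–76% | 3% |
| 1 | 41–46% | 75–76% | 8–9% |
| 2 | 2–3% | 73–75% | 49–59% |

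A repeat run gave 41% v 74% at D = 1, 3% v 75% at D = 2, and 58% in the last cell. A run with other assumptions (mean 3 real-world events, different subject SD) gave about 37% there.

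**Range at D = 1, r = 1.3 (planned v type-adjusted).**
- 2 real-world events each: 26–30% v 53–54%.
- 8 real-world events each: 57–62% v 89–91%.
- Real-world trip share 50%: 50–56% v 73–75%.
- Real-world trip share 95%: 29–33% v 76–78%.

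The 50% row matters for interpretation. With equal mixes the gap adds 0.25 to both variances, and the ratio still drops from 1.69 to (1.69 + 0.25)/1.25 = 1.55. Part of the power loss is therefore this dilution. The further fall, to 41–46%, comes from the mixes differing.

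**Opposite direction.** With the laboratory at 3:1, the real world at 50:50 and equal spread, the ratio at D = 2 is (1 + 0.25 × 4)/(1 + 0.1875 × 4) = 2/1.75 = 1.14. The planned test falsely supports Hypothesis 2 in 2–3% (D = 1) and 4–8% (D = 2), against a nominal 2.5%.

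**Limits of a type term.**
- *Chosen conditions.* If heights and hazards shift laboratory means by −0.5, 0 and +0.5 SD (assumed), they add (0.25 + 0 + 0.25)/3 = 0.17 to laboratory within-type variance. Type-adjusted power at r = 1.3 falls to about 38–40%.
- *Mislabelled events.* If 10% of real-world labels are wrong (assumed), real-world within-type variance gains 0.075D². With equal true spread, the apparent ratio is 1.07 at D = 1 and 1.30 at D = 2, and the type-adjusted test falsely favours Hypothesis 2 in 5–6% and 21–22%.

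**The case against.** The strongest reply is that the planned model fits the hypothesis. The Background rests Hypothesis 2 on varied causes, so event type is part of the variety claimed, and residuals without a type term measure exactly that. On that reading, lower power for within-type spread is power for a different question. This largely stands: a reader might infer that the planned test is wrong for Hypothesis 2, and the documents do not support that. What remains is that, even for total spread, the laboratory side depends on a trip-to-slip ratio that the investigators choose and the plan does not state.

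A second reply is that adjusting for type does not remove the investigators' influence, because the chosen heights and hazards stay in the within-type laboratory residuals. That is correct, and it limits what the added analysis can claim.

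Three further inferences go too far:
- *The test reverses the finding.* For the mix assumed here that needs D above about 2.8 at an SD ratio of 1.3.
- *The omission favours the hypothesis.* With a balanced laboratory mix and mostly trips outside, it works against it. The 3:1 example is near nominal at D = 1.
- *The Background shows that the recordings are unreliable.* Its remark on self-reporting concerns participant recall in prior studies, and the recorder is offered as the alternative. The documents give no label-error rate.

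**Conclusion.** The concern holds in a conditional form and should be settled before analysis. As specified, the comparison mixes response variability with the trip–slip gap, and it partly compares event mixes whenever p(1−p) differs between settings. It remains a legitimate total-spread analysis. It cannot attribute a difference, or the lack of one, to the responses rather than to the laboratory mix.

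Under the assumed mixes, the main risk is a hidden within-type difference: at D = 1 and SD ratio 1.3, roughly three chances in four of detection become about two in five. D, mixes, event counts, SD ratio and intraclass correlation are all assumptions, and D will differ between kinematic measures. If D is near 0, nothing changes.

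**What to change.** - Keep the planned test and interval as the total-spread analysis. Add the same test and interval on residuals from a model with LOB type and its interaction with environment, as the within-type analysis.
- State before analysis which of the two Hypothesis 2 rests on. The choice is the investigators'.
- Report event counts by type and environment.
- State that within-type laboratory spread still includes the chosen obstacle heights and slip hazards, and show laboratory spread by condition.
- Reconcile the recorder prompts. Section 4.1 asks for the activity, how balance was lost, why, and the result. Section 8.2 asks for the activity, the reason and the response, after a loss of balance of any kind. How balance was lost should always be recorded.
- Set a rule for events that are neither trip nor slip or cannot be classified.

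The cost is SAP wording, one model term with its interaction, and some tabulation. The recordings are already planned and carry a time and date stamp (Section 8.4). The downside is that real-world type is self-described, and mislabelling inflates real-world within-type spread. Note this as a limitation, with a simple check: repeat the within-type analysis with ambiguous recordings excluded, then assigned to each type in turn. A formal variance correction using the laboratory D is not advisable, because the interaction model lets D differ by setting.

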2.0 Objectives

2.1 Describe the purpose, specific aims, or objectives of this study:

The primary objective is to validate the use of wearable sensors for capturing responses to losses of balance (LOBs). During laboratory testing, we will use wearable sensors and a laboratory-based optoelectronic motion capture system to simultaneously measure responses to LOBs after laboratory-induced trips and slips. During real-world testing, we will use wearable sensors to measure responses to LOBs after any naturally-occurring trips or slips during the real-world daily lives of participants.

The secondary objective of this study is to compare the effects of three balance training exercises on responses to LOBs measured in the laboratory and in the real-world during daily life.

2.2 State the hypotheses to be tested:

Hypotheses for our primary objective that will involve non-balance training participants:

Hypothesis 1: LOB response measures obtained from the wearable sensors after lab-induced trips and slips will exhibit statistical agreement with the same measures obtained simultaneously from a laboratory-based optoelectronic motion capture system.

Hypothesis 2: Real-world LOB responses will show greater variety than laboratory-induced LOB responses.

Hypotheses for our secondary objective that will involve balance training participants:

Hypothesis 3: NT and TT participants will exhibit improved LOB responses after lab-induced trips and slips compared to ST participants.

Hypothesis 4: NT and TT participants will exhibit statistically-equivalent LOB responses after lab-induced trips and slips.

Hypothesis 5: NT and TT participants will exhibit improved LOB responses after any naturally-occurring real-world trips and slips.

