8.0 Procedures Involved

8.1 Describe and explain the study design:

For our primary objective, a one-group repeated-measures design will be used to validate the use of wearable sensors to capture responses to LOBs. Non-balance training participants will use wearable sensors for three weeks to capture responses to naturally-occurring trips and slips during daily life. Subjects will then complete a laboratory session to capture lab-induced LOB responses simultaneously from the wearable sensors and a gold-standard optoelectronic motion capture system.

For our secondary objective, a three-group posttest-only design will be used to compare the effects of three balance training exercises on responses to LOBs after laboratory-induced trips and slips, and two weeks of naturally-occurring real-world trips and slips. Balance training participants will first complete three weeks of their assigned training. Subjects will then complete a laboratory session to capture lab-induced LOB responses simultaneously from the wearable sensors and a gold-standard optoelectronic motion capture system. Subjects will then use wearable sensors for two weeks to capture responses to naturally-occurring trips and slips during daily life.

8.2 Provide a description of:

- *All research procedures being performed*
- *If the study has more than one procedure, session, and/or subject population, describe each procedure, session, and/or study*

population separately. For complex studies, you are encouraged to include a figure or chart.

Recruitment and Informed Consent

- Interested participants will respond to our recruitment strategies and contact the investigators.
- The investigators will telephone interested participants and follow the telephone script included in the application to first screen participants for inclusion criteria. If participants satisfy the inclusion criteria, the investigator will continue the telephone conversation and administer the health questionnaire described in an attachment to this application. De-identified information from this health questionnaire will then be reviewed by a health professional with specialist training for the geriatric population. This specialist will be a board certified physician or board certified specialist in geriatric physical therapy.

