14.0 Number of Subjects

14.1 Indicate the total number of subjects to be enrolled and how this number was determined (e.g., sample size calculation [show], number of available subjects in a finite pool, number of tests funding award would allow):

60 participants will be enrolled. This number is based upon a formal sample size analysis described here:

30 non-balance training participants will be recruited for our primary objective. Given that this objective is for validation, no formal effect sizes could be determined. Rather, we estimated 30 participants for this objective to be a reasonable number based upon our available resources and the number of expected LOBs estimated from prior work [Handelzalts et al. 2020].

30 balance training participants will be recruited for our secondary objective and be based upon Hypothesis 3: NT and TT participants will exhibit improved LOB responses after lab-induced trips and slips compared to ST participants.

The sample size was determined using data from lab-induced trips among community-dwelling older adults aged 65 years or older (Pavol et al., 2001). The effect size index (i.e., Cohen's $d = 1.45$) was determined using the difference in mean trunk angle from vertical at the time of recovery foot ground contact between fallers and non-fallers (17.4°) and the combined standard deviation (12°). The difference in means was considered the minimal clinically important difference based on the anchor-based method (Rai et al., 2015). Using G*Power (Faul et al., 2007) for an independent t-test with 80% power and a one-sided Type I error (or alpha) of 5%, a sample size of seven participants per group is needed. In an effort to be conservative and account for any participants withdrawing from the study, 10 participants per balance training group (TT,NT,ST) will be recruited.

Handelzalts, S., N.B. Alexander, N. Mastruserio, L.V. Nyquist, D.M. Strasburg, and L.V. Ojeda. Detection of Real-World Trips in At-Fall Risk Community Dwelling Older Adults Using Wearable Sensors. *Front Med*, 2020. 7: p. 514.

14.2 If this is a multi-site study, indicate the number of subjects to be enrolled at this site and the total to be enrolled from all sites:

21-1072 Validation and application of wearable sensors for capturing responses to losses of balance

Not a multi-site study.

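### Hypothesis 2: comparing event-level residuals weights people by how often they lose balance in the real world but about equally in the lab, which can bias the spread comparison in either direction

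*Combined protocol and SAP*

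**What the plan says.** Section 2.2 states Hypothesis 2 as a claim about spread: "Real-world LOB responses will show greater variety than laboratory-induced LOB responses". It is one of two hypotheses under the primary objective.

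Section 5.2 gives two steps. First, "a repeated-measures ANOVA (with a random effect for subject) will first be used to compare means of key kinematic measures of LOB responses" between settings. Second, "we will compare statistical variability by examining the model residuals between real-world and lab environments using hypothesis testing", described as Levene's test in essence, with interval estimation added. The section does not say how people with different numbers of events are weighted, whether the test allows for clustering by participant, or what happens to a participant with no real-world event.

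On the data:

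- Section 14.1: "30 non-balance training participants will be recruited for our primary objective".
- Section 8.1: "Non-balance training participants will use wearable sensors for three weeks to capture responses to naturally-occurring trips and slips during daily life". The number of real-world events per person is therefore whatever happens to occur.
- Section 14.1 justifies the sample partly by "the number of expected LOBs estimated from prior work", but gives no number.
- Section 8.2, on lab trips: "three trip obstacle heights from prior tripping studies will be used including 5, 7.5, and 10 cm". Three slip hazards are also listed. The number of induced events per person is not stated. Section 14.4 says that testing, apart from the training, is the same for everyone.

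**The concern.** A Levene-type test on event-level residuals gives each event one vote. In the real world a person's share of the votes is that person's share of the events. In the lab, if all follow the same protocol, the shares are about equal. The two spreads then describe different mixes of the same 30 people.

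The random subject effect does not correct this. It centres each person's responses, but a person whose responses are widely scattered stays widely scattered and counts in proportion to the number of events supplied.

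At stake is the attribution. Hypothesis 2 is about the setting. If frequent losers of balance are also more variable responders, the real-world residuals are wider even when every person responds with the same spread in both settings. If they are less variable, the real-world residuals are narrower and a true effect of setting can be masked. Each person is measured in both settings, so the spread comparison can be made within person, where this mix drops out.

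**Working it through.** The plan has no figure for Hypothesis 2 to reproduce. The seven per group in section 14.1 belongs to Hypothesis 3 and has no bearing here.

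**1. What the pooled comparison estimates.** Let person i have within-person SD σᵢ in both settings (no effect of setting), nᵢ real-world events and m lab events. Apart from the fitting of means:

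- lab mean square ≈ Σσᵢ² / 30
- real-world mean square ≈ Σnᵢσᵢ² / Σnᵢ

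With λ the event rate, the expected ratio is E[λσ²] / (E[λ]·E[σ²]) = 1 + Cov(λ, σ²) / (E[λ]·E[σ²]). It equals 1 if σ is the same for everyone or unrelated to λ. It exceeds 1 for a positive link and is below 1 for a negative one.

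**2. Assumed inputs.** From the documents: 30 people, and uncontrolled real-world counts. Assumed, because not stated: six lab events each; a mean of three real-world events; no subject-by-setting variance; σ = exp(h·z₁) and λ = 3·exp(g·z₂ − g²/2), with correlation ρ between z₁ and z₂. At ρ = 1, h = 0.3 and g = 0.7 mean that a person 1 SD above average has exp(0.7) = 2.0 times the events and exp(0.3) = 1.35 times the spread. For h = 0.2 and g = 0.5 the factors are 1.65 and 1.22. In this model the ratio in step 1 becomes exp(2hgρ).

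**3. Results.** True spread is equal in both settings, so every rejection is false. Ranges cover repeated simulations of 500 to 1,000 trials.

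| h, g | ρ | exp(2hgρ) | Pooled test rejects | Direction |
|---|---|---|---|---|
| 0, 0 | – | 1.00 | 5–6% | – |
| 0.1, 0.5 | 1 | 1.11 | 5–8% | – |
| 0.2, 0.5 | 1 | 1.22 | 16–20% | for Hypothesis 2 |
| 0.3, 0.7 | 0.5 | 1.23 | 19–20% | for |
| 0.3, 0.7 | 1 | 1.52 | 39–46% | for |
| 0.3, 0.7 | −0.5 | 0.81 | about 13% | mostly against |
| 0.3, 0.7 | −1 | 0.66 | about 40% | against |

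A regression of the absolute residual on setting, with a participant effect and participant-clustered standard errors, rejects in 4–7% of null trials.

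**4. A different model.** Gamma-distributed rates with a mean of 2 or 5 events, a coefficient of variation of person SD of 0.3, and six lab events gave:

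- correlation 0.5: variance ratio 1.26–1.39, false finding of greater real-world spread in 20–47%
- correlation −0.5: ratio 0.71–0.79, rejection 15–37%, nearly all against the hypothesis
- unequal rates unrelated to spread: ratio 0.98–1.04, rejection 7–11%
- same spread for everyone: ratio 1.02–1.03, rejection about 5%

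With each person weighted equally, and only people with real-world events used on both sides, the ratio was 0.94–0.99 throughout. In the unequal-rate settings the six most frequent of 30 people supplied 54–69% of real-world events, against 6/30 = 20% of lab events, and 17–45% of people supplied none.

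**5. Power when real-world SD is 1.5 times lab SD.**

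| Mean real-world events | Within-person test | Pooled test, no link |
|---|---|---|
| 3 | 84–92% | 94–97% |
| 1 | 38–48% | 67–70% |

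At a mean of one event, 37–45% of participants have no real-world event and leave the within-person test. At a mean of three with a fully negative link (h = 0.3, g = 0.7), the pooled test's power falls to about 40%.

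**The case against.** The strongest reply is that the bias needs two conditions: spread must differ between people, and it must be related to event frequency. The documents give evidence for neither. With equal spread, or a weak link, the pooled test holds close to its nominal level. This stands, and it limits the point to a risk of unknown size and sign.

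The largest figures come from a correlation of 1 between spread and rate, which is an extreme. This also stands, and the values at 0.5 and −0.5 are the fairer guide. At a mean of one real-world event the problem is smaller too: even at correlation 1, pooled false rejection was 8% (h = 0.2, g = 0.5) and 24% (h = 0.3, g = 0.7).

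Equal lab counts are inferred from the common protocol, and pooling is the default reading of a Levene test on residuals, not a stated choice. Both are fair. The wording leaves room for a better implementation but does not commit to one.

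A reader might go further and infer that a positive Hypothesis 2 result would reflect only who lost balance, or that the plan leans towards its own hypothesis. The documents do not support that: the link could be absent or negative, and a negative link works against the hypothesis. Nor is the within-person design wasted, since the subject effect already removes differences in person means.

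**Conclusion.** The point holds as a risk of bias in either direction. Read as pooled, the planned residual comparison uses different person weights in the two settings, and the subject effect does not correct this. How much it matters depends on a link between spread and event frequency that the documents do not inform. Under the assumed counts, false rejection runs from about 5% with no link, through about 13% and 19–20% at correlations of −0.5 and 0.5, to 39–46% at a correlation of 1. Even with no link, unequal event rates alone gave 7–11% in the second model, although the ratio itself was nearly unbiased. Confidence is moderate: the mechanism follows from the plan, but its size rests on assumed event counts and an assumed link. The change is worth making because Hypothesis 2 belongs to the primary objective and the link cannot be known in advance.

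**What to change.** In section 5.2, Hypothesis 2:

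1. Pre-specify a within-person spread comparison: regress the absolute residual on setting with a participant effect and participant-clustered standard errors, among participants with at least one real-world event.
2. Report the number of participants and events in each setting, and the distribution of events per person.
3. Present the pooled Levene comparison alongside, and do not attribute greater variety to the setting unless the within-person result agrees.

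This changes SAP wording and needs no new data. The cost is that participants with no real-world event leave the test. At a mean of three events the power loss is modest; at a mean of one it is large, so requiring agreement could then leave a true effect of setting unproven. The sponsor should therefore state in section 14.1 the expected number of real-world events per person, and in section 8.2 the number of lab events, so that the power of both comparisons can be judged beforehand.
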